## **Administrative information**

- 1. Title:** Assessment of Antimicrobial Efficacy of Nano Chitosan, Chlorhexidine, Chlorhexidine/ Nano Chitosan Combination versus Sodium Hypochlorite Irrigation in Patients with Necrotic Mandibular Premolars: A Randomized Clinical Trial
  
- 2. Trial registration:** This study was registered on **Protocol Registration and Results System (PRS)**.
  - Website: [www.clinicaltrials.gov](http://www.clinicaltrials.gov)
  - ClinicalTrail.gov ID NCT03668899.
  - Release Date: September 15, 2018.
  
- 3. Protocol version:** version 1.
- 4. Funding:** Totally Self-funding  
**Sponsor:** Cairo University, Faculty of Dentistry.
  
- 5. Trial roles and responsibilities:**

## 6. Introduction

### a. Description of the research question:

#### PICOS

**P** - Adult patients with necrotic mandibular premolars.

**I**- Interventions

**I1**: Irrigation with nano chitosan

**I2**: Irrigation with chlorhexidine

**I3**: Irrigation with Chlorhexidine/Chitosan combination

**C**- Irrigation with Sodium Hypochlorite.

**O**- Primary Outcome: Antimicrobial efficacy of the different irrigants.

Secondary Outcome: Postoperative pain.

**S**- Randomized controlled trial.

#### **Formulated question:**

In necrotic mandibular posterior teeth, would irrigating the canals using either Nano chitosan, Chlorhexidine or a combination of Nano chitosan and Chlorhexidine versus Sodium Hypochlorite have different effects on canal disinfection and postoperative pain?

#### **Statement of the problem:**

Bacteria play a major role in the pathogenesis of apical periodontitis; therefore, success of endodontic treatment is dependent on its complete eradication before obturation.

Sodium hypochlorite (NaOCl); the gold standard for irrigation has many disadvantages including irritation of the periapical tissues and burning of surrounding tissues. Therefore, the present study aims to explore new irrigating solutions probably more effective and less irritating to the periapical tissues than NaOCl.

#### **Rationale for carrying out the trial:**

Many studies have been conducted to assess the antimicrobial efficacy of sodium hypochlorite, (as a gold standard) compared to other suggested alternatives such as Chlorhexidine (CHX), both in vitro and in-vivo.

Zandi et al 2016, evaluated the antimicrobial efficacy of 2% Chlorhexidine compared to 1% Sodium hypochlorite irrigation in treating teeth with apical periodontitis and found that both solutions are similarly effective in reducing bacterial cell counts. The results of this study agreed with the results of a previous study that was conducted by Ercan et al on 2004 where the antimicrobial efficacy of 2% CHX was compared to that of 5.25% NaOCl in treating necrotic teeth with periapical pathosis and concluded that both solutions were significantly effective to reduce the microorganisms in the teeth with necrotic pulp, periapical pathologies, or both, and could be used successfully as an irrigant solution.

Regarding postoperative pain, Almeida et al 2012, evaluated postoperative pain after single visit root canal treatment using either 2% CHX or 5.25% NaOCl as irrigating solutions

and found a low incidence of postoperative pain in both groups with no statistically significant difference between them^8.

A recent study by Farzaneh et al evaluated the effects of two different concentrations of NaOCl ,2.5% and 5.25%, on postoperative pain after single visit endodontic treatment of molars with symptomatic irreversible pulpitis and found that 5.25% NaOCl irrigation resulted in significantly less postoperative pain in the first 72 hours postoperatively.

The current available evidence has inconclusive results when comparing the antimicrobial efficacy of NaOCl to CHX as suggested by a recent systematic review conducted by Goncalves et al 2016, they included only 5 clinical studies out of 172 reviewed articles and found that the results of the studies were inconsistent and recommended further clinical trials to reach conclusive results.

Recent studies has shed the light on a wide range of natural substances like Chitosan, Propolis, and other herbal solutions that are claimed to be as effective against bacteria as NaOCl, less toxic and less irritant and also introduced nanoparticles with their known antimicrobial capabilities as endodontic irrigants.

An in vitro study in 2017 claimed that the combination of 2% Chlorhexidine and 2% Chitosan is as effective as NaOCl against *E. Faecalis* in biofilms.

Since within the scope of our search no study evaluated the antimicrobial effects of Nano chitosan, Chlorhexidine/Chitosan combination as possible natural irrigants to those of NaOCl for irrigation in-vivo.

The **Aim** of the current study is to compare the antimicrobial effects of Nano chitosan, chlorhexidine, and their combination to NaOCl in patients with necrotic mandibular Premolars.

## Review of literature:

### Chemo-mechanical preparation:

It is well established that the most probable cause failure of endodontic treatment is the presence of a persisting infection. Therefore, it is important that chemo-mechanical canal preparation be directed towards complete eradication of all bacteria from the root canal system so that the best possible prognosis can be achieved in endodontic treatment.

“Only a few studies have evaluated the effect of infection at the time of root filling on the prognosis of treatment. These studies have shown that the success rate of endodontic treatment is approximately 10-15% lower for teeth which yield a positive culture before obturation than for teeth which yield a negative culture”.

**Dunavant et al 2006**, compared the efficacy of sodium hypochlorite to ,Smear Clear, Chlorhexidine, REDTA and BioPure MTAD against *E. Faecalis*. They submerged an in vitro grown *E. Faecalis* biofilm in wells containing either 1% NaOCl, 6% NaOCl, Smear Clear, 2% CHX, REDTA or BioPure MTAD for one and five minutes. Phosphate buffered saline was used as a negative control while 6% NaOCl was used as a positive control. After that the biofilms were re-cultured on THB agar plates and the number of colony-forming units (CFUs) was count. There was no significant difference between 1% NaOCl and 6% NaOCl yet, there was a significant difference between 1% and 6% NaOCl and all other tested irrigants with BioPure MTAD being the least effective solution.

**Perochena et al 2015**, studied the chelating and antibacterial effects of chitosan nanoparticles (CNPs) on bovine dentin. Five groups of bovine dentin sections (20 per group) were used in the study. They used 2.5% sodium hypochlorite (NaOCl) for 20 min, 17% ethylenediaminetetraacetic acid (EDTA) for 3 min and 1.29 mg/mL CNPs for 3 min as irrigating solutions. The groups were irrigated with distilled water as acontrol, NaOCl alone, NaOCl then EDTA, NaOCl then EDTA then CNPs or NaOCl then CNPs. After irrigation, half of the samples were used to assess the chelating effect of the solutions using scanning electronic microscopy, while the other half were infected intra-orally to examine the post-treatment bacterial biofilm forming capacity under confocal laser scanning microscopy. The results of this study showed that smear layer removal was significant in all of the groups except the control and NaOCl groups and that the samples treated with CNPs were resistant to biofilm formation significantly more than other treatment groups. Therefore, they concluded that CNPs irrigation was superior to NaOCl in that as well as inhibiting bacterial growth it also can remove the smear layer effectively.

**Rocas et al 2016**, evaluated the antibacterial effects of 2% chlorhexidine and 2.5 % NaOCl irrigation during rotary preparation of contaminated root canals. A total of 50 single rooted teeth with infected necrotic pulps were included in the study (two groups n=25). All root canals were prepared using BioRace rotary file system. Irrigation was done using either 2. NaOCl in one group or 2% CHX in the other group. Two samples were collected from

each canal S1 before chemomechanical preparation and S2 after chemomechanical preparation. In this study, the number of viable bacteria was determined by a quantitative polymerase chain reaction all initial samples (S1) were contaminated while in NaOCl group 44% of the treated canals were still contaminated and in CHX group 40% of the treated canals were contaminated. This difference was not statistically significant.

**Zandi et al 2016**, evaluated the antimicrobial efficacy of 2% chlorhexidine compared to 1% sodium hypochlorite used as irrigants in the retreatment of endodontically treated teeth with apical periodontitis. A total of 67 patients were randomly assigned to either 1% NaOCl group (n=29) or 2% CHX group (n=38). Three samples were taken from each tooth; S1 before preparation, S2 after preparation and irrigation with either of the tested irrigants and S3 after application of calcium hydroxide intracanal medication. The amount of bacterial reduction was evaluated using 16s ribosomal RNA gene-based polymerase chain reaction. The results of this study suggested that both solutions are similarly effective in reducing bacterial cell count.

**Jaiswal et al 2017**, evaluated antibacterial efficacy of Chitosan, Chlorhexidine, Propolis and Sodium hypochlorite on *E. Faecalis* biofilm invitro, Ninety single rooted mandibular premolars were included in the study. The root canals were then instrumented with rotary ProTaper instruments to an apical size of F3. 2 ml of 5% NaOCl was used as an irrigant during preparation. Teeth then vertically sectioned into two halves and divided into nine experimental groups with 20 samples each. irrigated with 3 ml of each irrigant for 10 minutes. Group 1: 5% NaOCl, group 2: 2% Chlorhexidine, group 3: 1% Acetic acid, group 4: Propolis, group 5: 0.2% Chitosan, group 6: 0.2%Chitosan+2%Chlorhexidine, group 7: 1% Chitosan+1%Chlorhexidine, group 8: 2%Chitosan+2%Chlorhexidine and group 9: Saline (negative control). The results of this study showed that Chitosan/ Chlorhexidine combination, Chlorhexidine and Propolis were as effective as sodium hypochlorite, so they concluded that their use as natural alternatives for NaOCl could be advantageous to overcome the disadvantages of NaOCl.

**Yadav et al 2017**, evaluated antibacterial effects and cytotoxicity of 0.25% Chitosan, 0.5% Chitosan, 2% chlorhexidine and 3% sodium hypochlorite against *E. Faecalis* and *C. Albicans*. *C. albicans* and *E. faecalis* cultures were prepared in vitro, then the antimicrobial activity of the tested solutions (0.25% Chitosan, 0.5% Chitosan, 2% CHX and 3% NaOCl) against them was evaluated using agar diffusion, microdilution and biofilm susceptibility tests. Saline was used as a negative control. For the cytotoxicity evaluation fresh blood was centrifuged then plasma was abstracted and packed cell volume of red blood corpuscles was obtained. Then 1 ml of packed RBCs was added to 4 ml of saline. 100 $\mu$ l of this diluted RBCs was distributed to 18 test tubes to obtain 3 groups (Chitosan, Chlorhexidine and hypochlorite), 6 test tubes each. For all groups, the first test tube was kept as a control in which no irrigant was added. In the second test tube 10  $\mu$ l of the irrigant was integrated. 20  $\mu$ l was integrated to the third test tube, 30  $\mu$ l to the fourth test tube, 40  $\mu$ l to the fifth test tube and 50  $\mu$ l to the test tube. Tubes were incubated for 3 minutes then hemoglobin percentage after hemolysis was detected utilizing an automated hemoanalyzer. The results of this study

suggested that chitosan could be used as a non-toxic natural alternative to NaOCl since the antibacterial activity of the all chitosan groups was comparable to 3% NaOCl and 2% Chlorhexidine and that the chitosan showed no cytotoxicity at 3mg/ml.

## **6. b. Choice of comparators:**

Sodium hypochlorite (NaOCl) was considered the most efficient of all available solutions for its superior antimicrobial effects and tissue dissolving abilities. Therefore, as a gold standard for irrigation; it was chosen as a comparator in the current study.

## **7. Objectives:**

### **- Research hypothesis:**

There is no difference in the antimicrobial efficacy among Nano chitosan, Chlorhexidine, Chlorhexidine/Nano Chitosan and Sodium hypochlorite in root canal treatment.

### **- Primary objective:**

The primary objective of this study is to assess the antimicrobial efficacy of Nano-chitosan, chlorhexidine and Chlorhexidine/Nano Chitosan combination versus NaOCl.

### **- Secondary objective:**

The secondary objective is to assess the incidence and severity of postoperative pain after root canal treatment using either Nano-chitosan, CHX, Chitosan/CHX combination or NaOCl as a final flush before obturation.

## **PICOS**

**P** - Adult patients with necrotic mandibular Premolars.

**I**- Interventions

**I1**: Irrigation with nano chitosan

**I2**: Irrigation with chlorhexidine

**I3**: Irrigation with Chlorhexidine/Chitosan combination

**C**- Irrigation with 5.25% sodium hypochlorite.

**O1**- Antimicrobial efficacy of the different irrigants.

**O2**- postoperative pain.

**S**- Randomized controlled trial.

## **8. Trial design:**

- A Randomized controlled clinical trial.
- Unicenter: A trial will be carried out by one person in one hospital.
- Randomization double blinded: Laboratory assessor and participant will not know the method of treatment.
- Equal randomization: participants with equal probabilities for intervention.
- Positive controlled: All groups receiving treatment.
- "Parallel group study: Each group of patients receives a single treatment simultaneously".
- Two assessors will assess the results.

### **III. Methods**

#### **A) Participants, interventions & outcomes**

##### **9. Study setting:**

- This study will be carried out on patients attending outpatient clinics in the Department of Endodontics, Faculty of Dentistry; Postgraduate Endodontics clinic 7th floor new section. Cairo University, Egypt. Adeq 200 U.S.A dental units.

##### **10. Eligibility criteria:**

###### **10. a. Inclusion criteria**

1. Patient's age between 22-42 years.
2. Both male and female.
3. Patient who are medically free and with good health
4. Necrotic Mandibular Premolars.

###### **10. b. Exclusion criteria:**

1. Pregnant females.
2. Teeth with vital inflamed pulps, symptomatic periapical abscess and facial cellulitis, periodontally diseased and hopeless teeth.
3. Teeth with previous fillings and/ or previous endodontic treatment.

#### **11. Interventions:**

##### **11. a. General operative procedures:**

- Eligible patients will be randomly divided into equal groups (Nano Chitosan group), (Chlorhexidine group), (Chlorhexidine/Chitosan combination group) and the control group (Sodium Hypochlorite group).

##### **- Preoperative measures (for all groups):**

- Medical and dental history will be obtained from all patients participating in this research. Clinical and radiographic evaluation for each tooth included in this study will be recorded.
- Pain scale chart will be given to each patient to rate his /her pain level before endodontic treatment as preoperative reading on an NRS scale.
- Tooth will be anaesthetized using 1.8 ml Mepivacaine HCl 2% - Levonordefrin 1:20000 (Carpule Mepecaine-L, Alexandria Company for Pharmaceuticals and Chemical Industries, Egypt).
- The tooth will be isolated with rubber dam to maintain aseptic field, after isolation the tooth and surrounding field will be disinfected by a protocol using 3% hydrogen peroxide 2.5% sodium Hypochlorite before and after coronal access cavity preparation.
- The initial sample S1 will be collected from root canals before preparation using sterile # 15 paper points.

- Sterile saline solution will be injected in the canals followed by the insertion of a #15 K-file (Mani, Japan) to at least 1 mm short of the apex as confirmed by apex locator (Root ZX, J.Morita USA, Irvine, CA) to facilitate the insertion of the paper points to collect the samples.
- Each paper point will remain in place for at least 1 minute then immediately placed in test tubes containing reduced transport fluid and sent to the Microbiology Laboratory, Faculty of Medicine, Cairo University for microbiologic processing.
- Root canals will be mechanically prepared in a crown-down approach using the rotary files (M-Pro file system) in an endodontic motor (X-Smart, Dentsply Maillefer, USA) according to the manufacture instructions.

The following sequence will be used for all groups:

- # 18 file taper (orifice opener) 0.09 will be used to prepare two thirds of estimated working length.
- # 20 file taper 0.04 will used to full working length.
- #25 file taper 0.06 will used to full working length.
- #35file taper 0.04 will used to full working length.
- The canals will be thoroughly irrigated for 1 minute between every two subsequent files using 2 ml of 2.5% NaOCl.
- After complete preparation all canals will be flushed with EDTA followed by sterile saline.
- **Intervention for test group A**
  - After complete preparation, the canals will be flushed using 5 ml of Nano chitosan (Nano tech, Egypt) in a plastic syringe using Navitip needles (Ultradent, South Jordan,UT).
- **Intervention for test group B**
  - After complete preparation, the canals will be flushed using 5 ml of Chlorhexidine (CHX-Plus, Cosmopack, Egypt) in a plastic syringe using Navitip needles (Ultradent, South Jordan,UT).
- **Intervention for test group C**
  - After complete preparation, the canals will be flushed using 5 ml of a combination of Chlorhexidine and nano chitosan in a plastic syringe using Navitip needles (Ultradent, South Jordan,UT).
- **Intervention for control group**
  - After complete preparation, the canals will be flushed using 5 ml of 5.25% sodium hypochlorite (Clorex, Egypt Ltd, Egypt) in a plastic syringe using Navitip needles (Ultradent, South Jordan,UT).
- After flushing the canals with each irrigating solution all canals are to be flushed with 10 ml sterile saline and the final sample S2 is to be collected in the same manner as S1.
- After dryness, root canals will be obturated using lateral compaction technique by selection of master cone corresponding to the same size as the master apical file, and then a finger spreader will be used to allow space for auxiliaries. All canals will be sealed with a resin sealer (ADSEAL, META Biomed CO., LTD Chungbuk, Korea).

- After obturation, a cotton pellet will be placed in the pulp chamber and the access cavity will be closed with a temporary filling.

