**12. Outcomes:**

**Primary outcome:**

- **Antibacterial efficacy:** will be assessed by counting the number of colony forming units (CFU) before and after irrigation (S1 and S2) for each patient. Collected samples will be cultured in serial dilution on blood agar plates, incubated for 24 hours, and then the number of colony forming units (CFUs) will be counted per ml.

Outcome	Tool	Unit	Time
antibacterial efficacy	Number of CFUs 	Numerical data	Samples collected before and after preparation and transferred to the laboratory for immediate cultivation.

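### The plan describes only dilution between the arm-specific flush and the S2 culture, so the primary CFU comparison may include killing that happens after sampling

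*Combined protocol and SAP*

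**What the plan says.** The final 5 ml flush is the treatment step that differs by arm: nano chitosan, chlorhexidine, the two combined, or 5.25% NaOCl (section 11.a). The next step reads: "After flushing the canals with each irrigating solution all canals are to be flushed with 10 ml sterile saline". S2 follows, taken by the S1 procedure, which is given earlier in the same section: "Sterile saline solution will be injected in the canals followed by the insertion of a #15 K-file", followed by paper points. On handling: "Each paper point will remain in place for at least 1 minute then immediately placed in test tubes containing reduced transport fluid".

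In section 12 the primary outcome "will be assessed by counting the number of colony forming units (CFU) before and after irrigation (S1 and S2) for each patient". The laboratory method is: "Collected samples will be cultured in serial dilution on blood agar plates, incubated for 24 hours", with results in CFU per ml. Section 18 repeats that colonies will be counted and adds nothing on sample handling. No section names an inactivating agent in the canal, transport tube, diluent or agar, and none plans a control for carry-over.

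**The concern.** A culture count measures what grows on the plate. To read S2 as disinfection of the canal, the agent must stop acting once the sample is taken. Here the paper point sits for at least a minute in a canal just exposed to that arm's own irrigant, and whatever it absorbs goes into the tube. If residue still inhibits growth there or on the plate, S2 records killing in the canal plus killing after sampling.

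The regimens are chemically different, so equal carry-over cannot be presumed. An agent that lingers could look better without any advantage in the canal, or a real difference could be masked. Using the change from S1 does not help, because S1 is taken before any arm-specific irrigant is used. The 2.5% NaOCl used during preparation is common to all arms and so is not itself a source of arm-specific residue. Assessor blinding does not help either: a blinded assessor counts correctly what grew.

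**Working it through.** **1. Path from flush to plate, as written**

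| Step | Section | Effect on residue described |
|---|---|---|
| 10 ml saline flush | 11.a | dilution |
| Further saline injected at sampling, #15 file | 11.a | dilution |
| Paper point into reduced transport fluid | 11.a | dilution; composition not given |
| Serial dilution, blood agar, 24 h | 12 | dilution, least on the first plates |

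No step is described as inactivating. Low S2 counts are read from the least diluted plates, which are the most exposed.

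**2. The plan's own figure.** Inputs from sections 14 and 20: difference 75, SD 75, two-sided 5%, power 80%. For a two-sample t-test with n per arm, the noncentrality is difference / (SD × √(2/n)), on 2n − 2 degrees of freedom.

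- n = 16: 75 / (75 × √(2/16)) = 2.83; power 78.1%.
- n = 17: 75 / (75 × √(2/17)) = 2.92; power 80.7%.

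So 17 per arm reproduces, and 17 / 0.85 = 20 matches the inflated number. The sample size is not in question here.

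**3. Illustration of the bias.** From the plan: SD 75 and n = 17. Assumed, because the documents give no values: no true difference between two arms; mean S2 of 150, 100 or 50 CFU; carry-over that suppresses 25%, 50% or 75% of colonies in one arm only, with the SD unchanged.

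False difference = mean × fraction suppressed. The chance of a significant result is the t-test power at that difference.

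| Assumed mean S2 | 25% suppressed | 50% suppressed | 75% suppressed |
|---|---|---|---|
| 150 | 37.5 CFU → 29% | 75 CFU → 81% | 112.5 CFU → 99% |
| 100 | 25 CFU → 16% | 50 CFU → 47% | 75 CFU → 81% |
| 50 | 12.5 CFU → 8% | 25 CFU → 16% | 37.5 CFU → 29% |

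The nominal rate is 5%. With 10% suppression at a mean of 150 (15 CFU) the rate is 9%.

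**4. Checks on the illustration**

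- The planned four-group ANOVA (section 20), with one arm affected and a mean of 150, gives 28%, 84% and 99.6%. The choice of test does not drive the result.
- At n = 20 and a mean of 150, the pairwise rates for 25% and 50% suppression rise to 34% and 87%. More patients make a false difference easier to detect; they do not remove it.
- On the log10 scale the shift is −log10(1 − fraction): 0.12, 0.30 and 0.60 for 25%, 50% and 75%, whatever the mean.

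**The case against.** The strongest reply is that silence is not proof. Samples go to a separate microbiology laboratory, the sampling and counting steps cite published methods, and the composition of the transport fluid is not given. The laboratory may inactivate residue as routine. This stands in part: a reader might infer that no inactivation will take place, but the documents support only that none is described. Even so, sampling, transport and plating are all set out, and following them as written leaves the comparison exposed.

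Second, a reader might infer that a single saline rinse is all that protects the culture. That is too strong. Further saline at sampling, transport fluid and serial dilution all reduce residue. Dilution is not shown to stop its action, however.

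Third, a reader might infer that the bias favours a particular arm. The documents do not support this. The literature review reports that dentine treated with chitosan nanoparticles resisted later biofilm. That makes unequal persistence plausible, but it does not measure release into a paper point or killing in a tube.

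Fourth, the rates depend on assumed inputs. The 50% case equals the planning difference only because 150 × 0.5 = 75. The SD comes from a study of primary teeth that, by its title, tested NaOCl but none of the three test irrigants. The review also cites a trial in which only 44% (NaOCl) and 40% (chlorhexidine) of canals were still positive after preparation, by a molecular method. Carry-over cannot suppress colonies where nothing survived. All of this stands, which is why a range is shown and no single rate is a forecast.

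**Conclusion.** The concern holds in a limited form. The plan describes dilution but neither inactivation nor a carry-over control, so a difference in S2 counts cannot be read cleanly as a difference in killing within the canal. The size is unknown. Under the stated assumptions the false-positive rate runs from 8% to 99%, and it stays near 5% if carry-over is small or similar across arms. The direction is also unknown, and a true difference could be hidden as easily as a false one created. The documents do not show that the bias will occur or which irrigant would gain. They show that the trial's own data could not detect it. Because the primary outcome is affected and the protection is cheap, the change should be made before sampling starts.

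**What to change.** In sections 11.a and 12, specify a neutraliser or neutraliser mixture chosen by the laboratory. Use the same one in all four arms, in both S1 and S2 tubes, and in the first dilution. If the laboratory already inactivates residue, state how.

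Before enrolment, run a bench recovery check for each of the four irrigants. Compare (a) inoculum + agent + neutraliser and (b) inoculum + neutraliser, each against inoculum alone. Comparison (a) shows whether the agent's action is stopped; (b) shows whether the neutraliser is itself inhibitory. That one product will cover all four regimens is not established in the documents, and section 11.a gives no concentration for the chitosan or the chlorhexidine, so the check is essential. If no neutraliser passes for an agent, state carry-over as a limit on reading S2 differences as in-canal efficacy.

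The cost is reagent for about 160 tubes (4 arms × 20 patients × 2 samples, at one tube per sample), one bench run and a sentence in each section. Recovery may fall slightly, and the bench check must show that this does not depend on the arm. No irrigant, volume or patient care changes.
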